7.11.5 Other Observations Related to Safety

7.11.5.1 Bone Mineral Density and Biochemical Bone Metabolism Markers

Analysis Set: Safety Analysis Set

Analysis

Variable(s) : T score [Min <= -2.500,

-2.499<= - <=-1.000,
-0.999<= - <= MAX]

Bone Mineral Density (g/cm²)

Percent Change from baseline on Bone [Min<= - <-7, -7<= - <=Max]

Mineral Density (%)

NTELOP (nmol BCE/L)

Bone Type Alkaline Phosphatase (μg/L)

Visit: Baseline , Week 12, 24

Analytical

Method(s) : For each variable except T score, summaries (1), (3), and (4) will be provided by treatment group.

For T score, summary (2), (3), (4), and (5) will be provided by treatment group.

(1) Summary of Parameters and percent Change from Baseline by Visit
Descriptive statistics for observed values for each visit and percent changes from baseline will be provided.
For categorical variables, frequency will be summarized by treatment group for each visit.

(2) Summary of Parameters and Change from Baseline by Visit
Descriptive statistics for observed values for each visit and changes from baseline will be provided.

(3) Case Plots
Plots over time for each subject will be presented.

(4) Mean Plot with Standard Deviations
For T score, mean of observed values and changes from baseline will be plotted by visit.
For other variables, mean of observed values and percent changes from baseline will be plotted by visit.

(5) Summary of Shift of T score
Shift table showing the number of subjects in each category at baseline and each post-baseline visit will be provided.

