5.1.2 Secondary Objectives

The secondary objective of this study is to evaluate the efficacy and safety of TAK-385 40 mg administered orally once daily for 24 weeks, compared with leuprorelin injection (once/4 weeks, 1.88 mg or 3.75 mg SC/time) in subjects with uterine fibroids.

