6.2 Justification for Study Design, Dose, and Endpoints

6.2.1 Justification for Study Population and Design

Menorrhagia is the most frequent symptom seen in patients with uterine fibroids. Patients with menorrhagia have to frequently replace sanitary products. In addition, prolonged menorrhagia can induce iron-deficiency anemia. Therefore, menorrhagia is the main cause of QOL deterioration¹. Surgery is performed for radical treatment of uterine fibroids. Drug therapy is used before surgery to alleviate anemia and to reduce the size of myoma^{2,3}. TAK-385 is thought to overcome the shortcomings of GnRH agonists commonly used in preoperative therapy. In this study, the improvement in the bleeding profile is examined for evaluation of improvement of QOL and efficacy of TAK-385 in patients with uterine fibroids.

The study is designed as a double-blind, parallel-group study to demonstrate the non-inferiority of TAK-385 compared with leuprorelin which is commonly used for the treatment of uterine fibroids. Since the period of general presurgical treatment for uterine fibroids is 3 months, which is stated to be a period for decreasing the size of myoma and improving anemia in some reports³, the evaluation period of drug efficacy for the primary endpoint is to be set as 3 months. However, since medication for more than 3 months may sometimes be needed as a maintenance therapy, evaluation of drug efficacy and safety for up to 6 months are to be set as secondary endpoints. In benign indications GnRH agonist administration exceeding more than 6 months is generally not permitted because it may cause BMD loss resulting from a decrease in estrogen level.

The Treatment for this study is set at 6 months to evaluate the safety of TAK-385 and the potential effect of TAK-385 on BMD compared to GnRH agonists in subjects with uterine fibroids and menorrhagia. A single-blind treatment period (with placebo) is also included to investigate if there is any potential placebo effect on baseline blood loss and pain assessment. In addition, the Follow-up is included for safety assessment, including assessment of the recovery of menstruation after discontinuation of active treatment.

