6.2.3.2 Secondary Endpoints

A decrease in menstrual blood loss is to be assessed to demonstrate whether or not the decrease in menstrual blood loss can be maintained after administration for up to 6 months. Blood concentration of HGB is selected as a secondary endpoint as it is an important parameter of the bleeding profile, as described above. Myoma and uterine reduction prior to surgery is one of the most important goals of drug therapy. For this reason, myoma and uterine volumes are assessed using transvaginal ultrasound. Clinical symptoms unrelated to menorrhagia but associated with uterine fibroids, and also QOL are assessed using the NRS and UFS-QOL.

With regard to safety assessment, the hypoestrogenic state associated with long-term use of GnRH agonists has been reported to reduce BMD. For this reason, the effect of TAK-385 on BMD is to be assessed using dual-energy x-ray absorptiometry (DXA). In addition to the assessment of BMD, biochemical bone metabolism markers (serum NTELOP and BAP) are also to be assessed as a supplementary parameter of BMD. Other commonly used safety endpoints, such as AEs and vital signs, are also included.

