9.3.3 Final Visit or Early Termination

9.3.3.1 VISIT 10 (Day 169) (or Early Termination)

The final visit during the Treatment will be performed on VISIT 10 (169 days after the initial dose of the study medication for the Treatment). The following procedures should be performed. If early termination occurs during the Treatment, the same procedures scheduled at VISIT 10 should be performed.

- Pregnancy test (urine)
- Physical examination
- Vital signs and weight
- Patient diary (collected)
- Transvaginal ultrasound (see Section 9.1.17).
- BMD
- UFS-QOL
- WPAI:GH
- Anemia-related measurements
- Clinical laboratory tests

- Pharmacodynamic measurements
- Biochemical bone metabolism markers
- Standard 12-lead ECG
- AE
- Concomitant medications
- Compliance of study drug administration
- PGx sample collection (perform only in subjects who consent and from whom the sample has not been collected [see Section 9.1.12])

For all subjects receiving study medication, the investigator or subinvestigator must complete the Subject Status eCRF page.

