13.1.5 Safety Analysis

The following analyses will be based on the safety analysis set.

(1) Secondary endpoint

Treatment-emergent adverse events

A TEAE is defined as an AE whose date of onset occurs on or after the start of study drugs for the Treatment.

TEAEs will be coded using the MedDRA dictionary. The frequency distribution will be provided using the system organ class (SOC) and the preferred term (PT) for each treatment group as follows:

- All TEAEs
- Drug-related TEAEs
- Intensity of TEAEs
- Intensity of drug-related TEAEs
- TEAEs leading to study drug discontinuation
- Serious TEAEs
- TEAEs over time

Laboratory test results, standard 12-lead ECGs, vital signs, weight, BMD and biochemical bone metabolism markers (serum NTELOP and BAP)

For continuous variables except BMD, the observed values and the changes from baseline will be summarized by treatment group for each visit using descriptive statistics. For BMD, the observed values and the percent changes from baseline will be summarized by treatment group for each visit using descriptive statistics. Case plots will also be presented for the observed values.

For categorical variables, shift tables showing the number of subjects in each category at baseline and each post-baseline visit will be provided for each treatment group.

(2) Additional endpoint

- Period from the last dose of study drug to return of menstrual cycles.

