		Study Day	Follow-up Day
Baseline	Study Day: 1	-80 - 1	
Week 2	Study Day: 15	2 – 22	< 15
Week 4	Study Day: 29	23 – 43	< 15
Week 8	Study Day: 57	44 – 71	< 15
Week 12	Study Day: 85	72 – 99	< 15
Week 16	Study Day: 113	100 – 127	< 15
Week 20	Study Day: 141	128 – 155	< 15
Week 24	Study Day: 169	156 – 183	< 15
Follow-up	Follow-up Day: 28	2 <=	15 – 42

12-lead ECG

Visit	Scheduled Study Day (days)	Time Interval (days)	
		Study Day	Follow-up Day
Baseline	Study Day: 1	-80 - 1	
Week 24	Study Day: 169	2 – 183	< 15
Follow-up	Follow-up Day: 28	2 <=	15 – 42

Biochemical bone metabolism markers and BMD

Visit	Scheduled Study Day (days)	Time Interval (days)	
		Study Day	Follow-up Day
Baseline	Study Day: 1	-80 - 1	

Visit	Scheduled Study Day (days)	Time Interval (days)	
		Study Day	Follow-up Day
Week 12	Study Day: 85	2 – 127	< 15
Week 24	Study Day: 169	128 – 183	< 15

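### BMD versus leuprorelin, one stated reason for the 6-month treatment period, is planned only as side-by-side arm summaries, with no between-arm difference or confidence interval

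*SAP*

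**What the plan says.** **Purpose.** Protocol 6.2.1 sets the treatment period at 6 months to evaluate safety and the "potential effect of TAK-385 on BMD compared to GnRH agonists in subjects with uterine fibroids and menorrhagia". The secondary objective (Protocol 5.1.2) is to "evaluate the efficacy and safety of TAK-385 40 mg administered orally once daily for 24 weeks, compared with leuprorelin injection". BMD is a secondary safety endpoint, and Protocol 6.2.3.2 states that "the effect of TAK-385 on BMD is to be assessed using dual-energy x-ray absorptiometry".

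**Analysis.** Protocol 13.1.5: "For BMD, the observed values and the percent changes from baseline will be summarized by treatment group for each visit using descriptive statistics". SAP 7.11.5.1 follows this with "Descriptive statistics for observed values for each visit and percent" changes from baseline, by arm. It adds the frequency of a percent change below -7%, case plots, mean plots with SDs, and a T-score shift table. SAP 7.1 defines the summary of a continuous variable as n, mean, median, SD, minimum and maximum, so no interval enters by default.

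**Windows.** In SAP 7.1.3, the table headed "Biochemical bone metabolism markers and BMD" assigns Study Days 2 to 127 to Week 12 (scheduled Day 85) and Days 128 to 183 to Week 24 (scheduled Day 169), both limited to Follow-up Day below 15. When several scans fall in one window, the one nearest the scheduled day is used. Protocol 9.3.3.1 adds: "If early termination occurs during the Treatment, the same procedures scheduled at VISIT 10 should be performed". Those procedures include BMD and the bone markers.

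**Discontinuation and missing data.** Protocol 7.5 lists, as a reason for discontinuation, a VISIT 7 BMD below 90% of baseline, or an investigator's risk-benefit decision to stop when BMD is above that level. SAP 7.1.4 imputes nothing unless otherwise specified, and specifies nothing for BMD.

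**The concern.** The protocol poses a comparative BMD question, and the trial randomizes against the right comparator to answer it. The supporting evidence before this trial was cross-study: Protocol 4.2 sets the phase 2 BMD change beside earlier reports for leuprorelin 3.75 mg, and Protocol 6.2.2 accepts the 40 mg dose partly because BMD change was expected to be comparable to that of GnRH agonists. This trial supplies the concurrent randomized comparison, yet no estimate of the difference, and no statement of its precision, is prespecified.

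Two further features affect the arm means that a reader would have to compare. Subjects with the largest Week 12 loss can be missing from the Week 24 mean. Scans taken after little exposure can enter the Week 12 mean. Either could distort the comparison if stopping differs between arms. Without a prespecified contrast, the choice of model, population and window would be made after unblinding.

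**Working it through.** **1. The plan's own sample size.** Inputs (SAP 6.0): 83.6% response in both arms, margin 15%, one-sided 0.025, power 90%.

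n = [2 × 0.836 × 0.164] × (1.960 + 1.282)² / 0.15² = 0.2742 × 10.507 / 0.0225 = 128.05, rounded up to 129 per group. Allowing 10% non-evaluable, 129 / 0.90 = 143.3, rounded up to 144.

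Both figures reproduce, but they concern the PBAC endpoint only. The documents give no SD, margin or precision target for BMD.

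**2. Which endpoints get a between-arm interval.**

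| Endpoint | SAP section | Between-arm 95% CI |
|---|---|---|
| Myoma and uterine volume | 7.8.2.2 | Yes |
| Hemoglobin | 7.8.2.3 | Yes |
| NRS | 7.8.2.4 | Yes |
| UFS-QOL | 7.8.2.5 | Yes |
| WPAI:GH (additional endpoint) | 7.8.3.3 | Yes |
| BMD | 7.11.5.1 | No |

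**3. Precision available for BMD.** Half-width = t(0.975, 2n−2) × SD × √(2/n). The SD of percent change is an assumption, taken as 2% to 4%.

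| n per arm | Half-width in SD units | SD 2% | SD 4% |
|---|---|---|---|
| 144 | 0.232 | 0.46 | 0.93 |
| 129 | 0.245 | 0.49 | 0.98 |
| 100 | 0.279 | 0.56 | 1.12 |

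The last two columns are percentage points. The data already planned would support an interval of about ±0.5 to ±1.0 points at about 130 per arm.

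**4. Week 24 mean.** A subject stopped on the VISIT 7 result has a scan near Day 85. An early-termination scan before Day 128 also falls in the Week 12 window, so she has no Week 24 value. Only a termination scan on Day 128 or later, within the follow-up limit, would count as Week 24. If a share g is stopped, with mean loss L_s at Week 24 had they continued, against L_r in the rest, the observed mean understates loss by g × (L_s − L_r). This is positive when those stopped were losing more. The documents give no g, so no size can be set.

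**5. Week 12 window.** It reaches 85 − 2 = 83 days before the scheduled day and 127 − 85 = 42 days after. Because the nearest scan is used, an early scan counts only for a subject with no scan nearer Day 85, in practice one who stopped before VISIT 7. Assume loss proportional to d/85, and a share f of Week 12 values coming from scans on Day d. The fraction of the Week 12 loss hidden is f × (1 − d/85):

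- f = 0.05, d = 60: 0.05 × 0.294 = 1.5%
- f = 0.10, d = 40: 0.10 × 0.529 = 5.3%
- f = 0.15, d = 20: 0.15 × 0.765 = 11.5%

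For an assumed true Week 12 loss of 2% to 4%, that is 0.015 × 2 = 0.03 to 0.115 × 4 = 0.46 percentage points within an arm.

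The Week 24 window starts at Day 128, so the Day 2 limit cannot affect it.

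**The case against.** The strongest reply is that the SAP does what the protocol prescribes. Protocol 13.1.5 plans descriptive BMD statistics and the SAP follows. No safety analysis in SAP 7.11 has a between-arm interval, and the endpoints that do have one are efficacy endpoints. Some efficacy and pharmacodynamic variables (hematocrit, iron, ferritin, analgesic use, hormones) also have none. This stands: there is no contradiction between the documents. It does not dispose of the point, because an interval can be descriptive. SAP 7.8.2.1 labels its own intervals that way.

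A reader might infer that the BMD question goes unanswered. The documents do not support that. Both randomized arms are summarized at Weeks 12 and 24, and anyone can form an unadjusted difference and interval from n, mean and SD.

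A reader might also infer that the Day 2 limit undermines the 24-week comparison, or that it conflicts with the ultrasound window, whose Week 12 starts at Day 72. Neither holds. The limit touches only the Week 12 row. Starting the first post-baseline window at Day 2 is the SAP's general convention, and ultrasound has earlier scheduled visits where BMD has none. The Handling Rules for Analysis Data, which decide what data are acceptable, are not part of the two documents and might restrict early scans further.

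Nor is BMD the sole reason for the trial's length: Protocol 6.2.1 also cites overall safety and the occasional need for maintenance treatment beyond 3 months.

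Finally, the VISIT 7 scans of stopped subjects are already in the Week 12 row. That is true, but it does nothing for the Week 24 mean.

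**Conclusion.** The concern holds in a limited form. The protocol states a comparison of BMD with GnRH agonists, and the plan delivers it only side by side, without a prespecified contrast or precision. This is a gap worth closing cheaply. It is neither an error in the documents nor a threat to the primary analysis.

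The achievable half-width of about 0.5 to 1.0 percentage points rests on assumed SDs of 2-4% and about 130 subjects per arm. Selective loss from the Week 24 mean runs toward understating loss; its size cannot be determined from the documents.

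The window effect is secondary and confined to Week 12. The range of 1.5-11.5% rests on linear loss, 5-15% early scans and scan times of Day 20-60, none of which the documents give. For an assumed Week 12 loss of 2-4%, it stays below the half-width of the interval at about 130 per arm. If early stopping were alike in both arms, it would, under the same linear assumption, only shrink the contrast in proportion. It matters more if stopping differs between arms.

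**What to change.** **SAP 7.11.5.1.** Add the difference (TAK-385 minus leuprorelin) in percent change in BMD at Weeks 12 and 24, with a two-sided 95% CI labelled descriptive. Preferably take it from a repeated-measures model with treatment, visit, treatment-by-visit and baseline BMD. Such a model uses the observed Week 12 value of subjects stopped under the VISIT 7 criterion when it estimates the Week 24 difference. It assumes that, given the observed BMD, stopping does not depend on the unobserved values. That is plausible where the scan result itself triggered the stop, and less certain where a broader risk-benefit judgement did. At minimum, add the t-based interval already defined in SAP 7.1. That supplies the precision but leaves the Week 24 selection untouched.

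**SAP 7.1.3.** Start the BMD and bone-marker Week 12 window nearer Day 85, for example at Day 72, and show earlier early-termination scans in a separate row.

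**Cost.** SAP wording and one extra table, settled before unblinding, with no new data and no change in sample size. The downside is that a few early scans leave the Week 12 row.

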7.11.5.2 Return of Menstrual Cycles

Analysis Set: Safety Analysis Set

Analysis

Variable(s) : Duration of Menstruation Recovery (Days)

Analytical

Method(s) : Summary (1) will be provided by treatment group.

(1) Summary of Duration of Menstruation Recovery

Descriptive statistics for observed values will be provided.

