6.2.3.3 Additional Endpoints

In addition to blood concentration of HGB, HCT and serum concentrations of Fe and ferritin are also measured for the assessment of anemia during the Treatment. As analgesics are permitted in this study under specific conditions, information on analgesic use is incorporated into the efficacy assessment. Also, WPAI:GH, validated questionnaire to measure impairments in work and activities⁵, is used to evaluate the effects of TAK-385 on the QOL of patients with uterine fibroids.

Amenorrhea is induced due to the pharmacological effect of TAK-385. Therefore, in order to assess the time until menstruation returns after the end of treatment, the period from the last dose of study drug to return of menstrual cycles was selected as one of the other endpoints for additional assessment of the safety of TAK-385.

For the additional evaluation of the safety and efficacy of TAK-385 and pharmacodynamics of TAK-385 (LH, FSH, E₂, and P concentrations) in subjects with uterine fibroids are also to be evaluated.

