9.1.21 Status of Menstruation Recovery

If the first menstruation after the end of study drug administration is observed before the VISIT 11 in the Follow-up, the date of onset of the first menstruation is recorded in the eCRF. If menstruation recovery is not observed by the VISIT 11 in the Follow-up, follow-up will be continued as far as possible through telephone calls or other means until the recovery of the first menstruation. If menstruation recovery is observed during continued follow-up, the date of recovery should be recorded in the eCRF. The status at the end of menstruation follow-up will be recorded in the eCRF regarding menstruation recovery. After the Follow-up, follow-up will not

be continued in subjects who undergo surgery or receive hormone therapy for the treatment of uterine fibroids before the recovery of menstruation.

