Similarly, use of analgesic medications during the treatment from Week 2 to 6 and from Week 18 to 24 will be defined as proportion of days with analgesic use between Day 15 and earlier of Day 42 or Follow-up Day 3 and between Day 127 and earlier of Day 168 or Follow-up Day 3, respectively.

Use of analgesic medications during the Treatment for 6 weeks before the final dose

((number of days with analgesic medications use for the last 42 days of the treatment)/(number of days with available data for the last 42 days of the treatment))*100 (rounded to 1 decimal places)

Proportion of subjects with a total PBAC score of < 10 from Week 6 to 12:

((number of subjects with a total PBAC score of less than 10 from Week 6 to 12)/(number of subjects with available PBAC score from Week 6 to 12))*100 (rounded to 1 decimal places)

Myoma volumes

$D1*D2*D3*\pi/6$ (cm³)

Uterine volumes will be similarly calculated.

Definitions of D1, D2 and D3 are shown in protocol.

Duration of Menstruation Recovery

Date of menstruation recovery - date of last dose of double-blind study drug

Oral iron preparation

The drug with the following drug code of WHODD:
00023503001, 00023505001, 00023520001, 00023550009, 00023550074, 90059601001

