7.8.3.4 Amenorrhea (The subject with a total PBAC score of 0)

Analysis Set: Full Analysis Set

Analysis

Variable(s): Proportion of subjects with a total PBAC score of 0 from Week 6 to 12
Proportion of subjects with a total PBAC score of 0 from Week 2 to 6
Proportion of subjects with a total PBAC score of 0 from Week 18 to 24
Proportion of subjects with a total PBAC score of 0 for 6 weeks before the final dose of study drug

Analytical

Method(s): For each variable, frequency will be summarized by treatment group.
The point estimate and 2-sided 95% confidence interval of the difference in the percentage will be calculated between TAK-385 40 mg group and leuprorelin group, using FM method with the non-inferiority margin of -15%. The confidence interval will be presented in a descriptive manner and not for the purpose of statistical inference.

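### The return-of-menstruation summary is not split by whether menstruation was suppressed at the end of treatment, so it may mix reversal of amenorrhea with ordinary next periods

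*SAP*

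**What the plan says.** Protocol 6.2.3.3 gives the reason for the endpoint. It states that "Amenorrhea is induced due to the pharmacological effect of TAK-385", and that the period to return of menstrual cycles was therefore chosen "in order to assess the time until menstruation returns after the end of treatment".

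The recorded event carries no such premise. Under Protocol 9.1.21 the onset date goes into the eCRF "If the first menstruation after the end of study drug administration is observed before the VISIT 11 in the Follow-up"; otherwise follow-up continues, by telephone if needed, until menstruation returns. SAP 7.1.1 defines the duration as "Date of menstruation recovery - date of last dose of double-blind study drug". SAP 7.11.5.2 names the analysis variable as "Duration of Menstruation Recovery (Days", sets "Analysis Set: Safety Analysis Set" and, as the method, "Descriptive statistics for observed values will be provided", by treatment group.

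The SAP already derives bleeding status at the end of treatment. SAP 7.1.1 defines a total PBAC score for the last 42 days of treatment. SAP 7.8.2.1 uses it with a cut-off of 10, and SAP 7.8.3.4 includes "Proportion of subjects with a total PBAC score of 0 for 6 weeks before the final dose of study drug". Neither is used in 7.11.5.2.

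**The concern.** The protocol wants to know how long the drug-induced absence of menstruation lasts once the drug is stopped. For a woman still menstruating at the end of treatment, the interval from last dose to next period is largely the time left in her current cycle. It is entered in the same column, under the same label, as a suppressed woman's recovery time.

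The resulting mean and median describe two groups in unknown proportion. If the unsuppressed group has the shorter times, the summary understates how long reversal takes. If the proportion also differs between arms, part of any difference between the arms reflects bleeding control rather than reversibility. Readers are likely to take this table as the trial's evidence on reversibility.

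**Working it through.** **Plan's own figures.** The documents state no figure for return of menstruation. The nearest are in the sample-size section (Protocol 13.3, SAP 6.0): 83.6% expected with PBAC below 10 from Week 6 to 12 in both arms, 129 evaluable and 144 randomised per arm. These reproduce with the unpooled formula: (1.960 + 1.282)² × 2 × 0.836 × 0.164 / 0.15² = 128.05, rounded up to 129; 129 / 0.9 = 143.3, rounded up to 144.

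**Inputs.**
- Share not suppressed: 1 − 0.836 = 0.164, or 0.164 × 144 = 23.6 women per arm. This is a proxy, because it refers to Week 6 to 12 and not to the weeks before the last dose.
- Support for the cut-off: Protocol 6.2.3.1 reports that, of 2, 10 and 75, a PBAC cut-off of 10 agreed best with the number of menstruations (none versus one or more).
- Wait to the next period in an unsuppressed woman: assumed. With cycle length C uniform on the 25 to 38 days of the entry criteria and the last dose at a random point in the cycle, the mean wait is E[C²] / (2E[C]) = 1006.3 / 63 = 16.0 days. Half of a fixed 25- or 38-day cycle gives 12.5 or 19 days as a range.
- Mean recovery time R in suppressed women: not in the documents; assumed to be 30, 60 or 90 days.

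**Shortening of an arm's mean.** The mixture mean is 0.836R + 0.164w, where w is the mean wait. It lies below R by 0.164 × (R − w).

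| Assumed R (days) | w = 16 | w from 19 to 12.5 |
|---|---|---|
| 30 | 0.164 × 14 = 2.3 | 1.8 to 2.9 |
| 60 | 0.164 × 44 = 7.2 | 6.7 to 7.8 |
| 90 | 0.164 × 74 = 12.1 | 11.6 to 12.7 |

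The sign depends on R exceeding w. If the two were equal, there would be no shortening.

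**Median.** A simulation used gamma-distributed recovery times (shape 9, mean 60 days) in suppressed women and, in the others, a wait uniform over a cycle of 25 to 38 days. The median was 57.8 days in suppressed women alone and 53.0 days in the mixture at 83.6%. Reporting the median does not remove the effect.

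**Between arms.** With the same R and w in both arms, the spurious difference is (difference in suppression rates) × (R − w).
- At the planned rates, 83.6% in each arm: 0 × (R − w) = 0.
- For a hypothetical gap of 15 percentage points, a size borrowed from the non-inferiority margin: 0.15 × 14 = 2.1, 0.15 × 44 = 6.6 or 0.15 × 74 = 11.1 days, with the less suppressed arm appearing faster.

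**The case against.** The strongest reply is that the plan analyses the endpoint it defined. Protocol 5.2.3 and SAP 5.3 describe the period from last dose to return of menstrual cycles, with no suppression condition. Summarising all treated women keeps the randomised groups together, whereas a suppressed-only subset is formed after randomisation and its make-up depends on treatment. This stands as a reason to keep the safety-set summary. It is not a reason to leave it unsplit, because the stated purpose is reversal of amenorrhea.

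Several limits on size also stand.
- **16.4% is not a rate of women never suppressed.** Two moderately stained pads in six weeks score 2 × 5 = 10 and make a woman a non-responder, against an entry threshold of 120 per cycle. Protocol 6.2.3.1 also anticipates metrorrhagia under treatment. The figure is an upper proxy.
- **The 16-day wait is assumed.** The 25 to 38 day range is a pre-treatment entry criterion; nothing shows that women bleeding on a GnRH agent keep such cycles.
- **Early leavers are ambiguous.** A reader might infer that a woman who stops in the first weeks has nothing to recover from. The documents do not support that for leuprorelin: it is injected every 4 weeks, and Protocol 4.1 says agonist effects may take about 3 to 4 weeks to emerge. She may become suppressed after her last injection.
- **Consequence is modest.** This is an additional endpoint with no test, difference or confidence interval planned, and suppression by arm is tabulated elsewhere in the SAP. Those tables, however, do not show recovery times by suppression status.

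Analysis-set definitions are left to the Handling Rules for Analysis Data, which are not among the documents reviewed. They could contain a restriction, but neither the protocol nor the SAP states one.

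**Conclusion.** The point holds as a matter of description. SAP 7.11.5.2 pools women without regard to suppression at the end of treatment, so its by-arm summary may mix reversal of amenorrhea with ordinary next periods. If suppressed women take longer to menstruate, the mean and median are shortened. On the upper proxy of 16.4% and the 16-day wait, the fall in the mean is at most about 2, 7 or 12 days for an assumed R of 30, 60 or 90 days. These are illustrations, since the documents contain no recovery times.

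A reader might go further and infer that the arm with poorer suppression will look more reversible. The documents do not support that as a prediction. Both arms are planned at 83.6%, and with equal recovery in suppressed women the spurious difference is then zero. It arises only if suppression rates differ between arms. If true recovery times also differ between arms, the mixing distorts that difference rather than creating it.

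The primary analysis is untouched. The change is worth making because the table as planned does not isolate the quantity the protocol says it wants.

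**What to change.** In SAP 7.11.5.2, keep the summary in the Safety Analysis Set and add rows by treatment group:
1. Women with at least 42 days of treatment, split by total PBAC below 10 versus 10 or more over the last 42 days of treatment. This is the main split, because 10 is the cut-off that Protocol 6.2.3.1 supports.
2. The same women split by total PBAC of 0 versus above 0, as a supporting split. One lightly stained pad scores 1, so this definition is strict.
3. Women with fewer than 42 days of treatment, in their own row.

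Give the number of women in each row by arm, and state that the interpretation of reversibility rests on the suppressed row. If the Handling Rules already contain a restriction, state it in the SAP.

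The cost is one extra descriptive split on flags the SAP already derives, with no new data and no effect on sample size or the significance level. The downside is that the rows are post-randomisation subgroups with smaller numbers, so comparisons between arms within a row should be read as descriptive.
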